#### V. Discoloration

If while on-eye, any discoloration is observed, remove lens and confirm discoloration using the following classifications:

- 0 None
- 1 Faded
- 2 Yellow
- 3 Brown
- 4 Pink

#### 4.0 Method for the Examination, Description and Classification of Lens Fit

The following procedure has been developed to assist in the examination, description, and classification of contact lenses fit at all visits in the Investigator's office.

Materials needed: Slit Lamp

Procedure: Each lens should be examined on the eye using the slit lamp

employing a 7X to 15X magnification.

Lens fit will be assessed utilizing the scales below:

# **I.** Lens Centration (Enter Rating 0-3)

# **Qualitative Lens Centration**

- Compare lens edge overlap of limbus in all visible sectors.
- The centration diagram is pictured as lateral decentration toward 9:00 on the clock dial. Centration assessment applies to all clock hours.
  - o If the limbus is an ill-defined band, assess from the center of the band.
  - o If the contact lens edge translates with blinking, assess to the average lens edge position.
  - o Centration assessment applies to primary gaze.
  - o If the inferior edge of the contact lens is not visible, gently pull the lower eyelid away.
- Rate and record lens centration on a scale of 0 to 3 based on the following lens diagrams and descriptors:
  - 0) Equal Overlap 360 degrees
  - 1) Maximum overlap  $\leq 2/3$  in any sector
  - 2) Maximum overlap > 2/3 in any sector
  - 3) Any Corneal Exposure

#### II. Lens Movement

- As the subject blinks normally, observe lens movement, with particular attention to the inferior portion of the lens.
  - All movement depicted in the diagram below is from the absolute centered position.
  - All movement descriptions apply from the various decentered positions.
  - o Corneal exposure in any sector is an unacceptable fit.
  - o If the inferior edge of the contact lens is not visible, gently pull the lower eyelid away.
- Rate and record lens movement on a scale of -2 to +2 based on the following lens diagrams and descriptors:
  - -2 No observable movement (perform Josephson push-up test, see below)
  - -1 Minimal; Just observable movement, lens returns to origin.
  - Optimal/Free movement, lens returns to origin.
  - +1 Substantial movement; but lens does not immediately return to origin.
  - +2 Excessive movement; lens does not return to origin, may result in corneal exposure.

# Josephson Push Up Test

- Use Josephson Push-up test when specified or indicated (-2 = No observable lens movement, see lens movement ratings above).
  - Apply gentle upward digital pressure to the lower lid such that the lower lid margin pushes on the inferior aspect of the contact lens edge.
- Determine if this action causes the contact lens to move and rate as follows:
  - 1 Lens is mobile
  - 2 Lens is immobile

# BAUSCH+LOMB

# PRIMARY GAZE LENS CENTRATION

# PRIMARY GAZE LENS MOVEMENT

#### 5.0 **Symptoms and Complaints**

- 1. The question asked by the technician or ECP, "Are you experiencing any symptoms or problems with these lenses?"
- 2. If no is checked, all symptoms are registered as 0.
- 3. If the subject says yes, the technician or ECP asks "What specifically are you noticing?" The subject is not shown the list of options/descriptions. From the subject's response, the technician or ECP selects the most appropriate symptom and asks the subject to rate it on the following scale:
  - a. 0 No Symptoms
  - b. 1 Slight symptom; just feel or notice symptom occasionally
  - c. 2 Mild symptom; noticeable but not irritating or limiting use
  - d. 3 Moderate symptom; is irritating or annoying, use of device being limited by <25% (short wear time, etc.)
  - e. 4 Severe; very irritating or annoying, lens cannot be tolerated

#### Data Table:

"Are you experiencing any symptom or problems with these lenses?"

OD: Y

N

OS: Y

N

OD	Symptom	os
0-4	Discomfort	0-4
0-4	Excessive tearing	0-4
0-4	Photophobia	0-4
0-4	Halos	0-4
0-4	Itching/Burning	0-4
0-4	Spectacle blur	0-4
0-4	Variable vision	0-4
0-4	Blurred vision	0-4
0-4	Lens needs cleaning	0-4
0-4	Handling	0-4

# 6.0 Subjective Assessment Scales

Subjects should be provided the Rating Scales (separate document) to refer to while responding to the assessments being collected. Enter rating from 0-100 (eg, 90).

At Screening/Dispensing only, the following abbreviated assessments are to be collected for Study Lenses/Study Drops:

[figure not shown]

For all Follow-up visits, the following assessments are to be collected for Study Lenses/Study Drops:

# APPENDIX C: CORNEAL INFILTRATES EVALUATION FORM

Infiltrate Size (Largest): OD: \_\_\_\_(X.X mm) OS: \_\_\_\_(X.X mm) **Infiltrate Depth (Deepest):** OD: \_\_\_\_ OS: \_\_\_\_ 1. Epithelial 2. Anterior Stroma 3. Full thickness **Infiltrate Density:** OD: \_\_\_\_ OS: \_\_\_\_ Grade Description 0 None 1 Faint 2 Moderate (iris/lens details clear) 3 Marked (iris/lens details hazy) 4 Intense (iris/lens details obscured) **Infiltrate Type:** OD: \_\_\_\_ OS: \_\_\_\_ Grades 0 None 1 Micropunctate 2 Macropunctate 3 Coalesced Macropunctate 4 Patch **Ocular Discharge:** OD: \_\_\_\_ OS: \_\_\_\_ 1. None 2. Mucopurulent (green or yellow in color) 3. Whitish 4. Watery Degree of Pain: OD: OS:

0-10 Numeric Pain Rating Scale

Size of any overlying defect:

OD: \_\_\_\_(X.X mm) OS: \_\_\_\_(X.X mm)

[figure not shown]
# **Location:**

Check all that apply

OD:

- ☐ Central (central 6 mm, 3 mm from corneal center)
- □ Nasal
- $\square$  Inferior
- ☐ Temporal
- ☐ Superior

[figure not shown]
# Draw:

OS:

- ☐ Central (central 6 mm, 3 mm from corneal center)
- $\square$  Nasal
- $\square$  Inferior
- ☐ Temporal
- ☐ Superior

#### Draw:

#### APPENDIX D: CULTURE PROCEDURE

NOTE: The site must use their standard of care culture kit and ship specimens to their local laboratory for testing per the local lab's required procedures. Hard copy results must be filed in the subject record and entered into the eCRF.

#### PROCEDURES FOR THE INVESTIGATOR

A. In the case of corneal ulcer or suspected ocular infection, the cul-de-sac, lower lid margin, and the corneal lesion (if applicable) of the affected eye must be cultured.

#### 1. Cul-de-sac Culture

- a. The swab from a culture collection kit is moistened in sterile, physiological saline solution, with no preservatives.
- b. The ocular specimen is obtained by holding the lids open and asking the subject to gaze upward. The moistened swab should be drawn across the culde-sac while rotating the swab 360 degrees around the axis of the stick. Care should be taken to avoid contact of the swab with the lashes and the lid margins.
- c. Place the swab in the transport tube media according to manufacturer's directions.
- d. Repeat steps a through c using a separate swab and a separate tube of transport media for the other eye if both eyes require culturing.

# 2. Eyelid Culture

- a. The swab from a culture collection kit is moistened in sterile, physiological saline solution, with no preservatives.
- b. The specimen is obtained from the margin of the lower lid by drawing the swab along the margin of the lid.
- c. Place the swab in the transport tube media according to manufacturer's directions.
- d. Repeat steps a through c using a separate swab and a separate tube of transport media for the other eye if both eyes require culturing.

#### 3. Corneal Culture

- a. The swab from a culture collection kit is moistened in sterile, physiological saline solution, with no preservatives.
- b. The specimen is obtained from the corneal lesion by rotating the swab on the lesion for 10 seconds.
- c. Place the swab in the transport tube media according to manufacturer's directions.
- d. Repeat steps a through c using a separate swab and a separate tube of transport media for the other eye if both eyes require culturing.

- B. Labeling and Transportation of Cultures to the Clinical Laboratory:
  - 1. Complete the report form supplied by the central laboratory included with the culture collection kit. Affix labels supplied in the culture collection kit to the ocular specimens as well as to the container used to transport the contact lens case (which contains the contact lens[es] and contact lens case solution) if available.
  - 2. The specimens, contact lens(es), lens case(s), lens case solution(s) and report form are then sent to the central laboratory under refrigerated conditions using the supplies provided by the central laboratory.

#### APPENDIX E: SUBJECT INSTRUCTIONS – SOFT CONTACT LENSES

# **Rewetting Drop Subject Instructions**

#### PLEASE READ INSTRUCTIONS CAREFULLY AND KEEP FOR FUTURE USE

You will be participating in a study evaluating the safety and effectiveness of an Investigational Lubricating and Rewetting Drop compared to a marketed rewetting drop. Please keep all appointments and **follow these instructions thoroughly**. If you have any questions or problems, consult your study doctor.

**NOTE:** It is important to wear your study lenses to each of your follow-up visits and place 1 to 2 drops of rewetting solution in each eye about 30 to 60 minutes before each scheduled study visit.

#### **STUDY PRODUCT INFORMATION:**

For this study, you will be using the following products:

# • Study Rewetting Drops

• You will receive 1 carton that will contain either 6 multi-dose bottles or 56 pouches of 5 single-use dispensers.

#### • Study Contact Lenses

- You will be provided with 2 new pairs of your current contact lenses at the start of the study. One pair will be used as back-up, only if needed.
- Other Study Supplies. The following supplies will be provided to you as needed:
  - o One 10 FL OZ bottle of Biotrue multi-purpose solution.
  - Study Lens Cases. You are required to use only the lens cases provided during the study. You will be provided three lens cases, one to store your lenses for disinfection after wear and two for lens replacements if needed.
  - o **Zippered Bag.** To hold empty multi-dose rewetting drop bottles or opened single-use dispensers.
  - o **Subject Instructions.** A copy of this sheet to be included.
- Carton/Bottle/Single-Use Dispenser Return Materials. Opaque, drawstring bag to place all study materials into, including Study Kit (carton) with unused study rewetting drops, zippered bag for returning partially full, and empty multidose drop bottles or opened single-use dispensers along with all worn and unworn lenses.

#### SUBJECT INSTRUCTIONS (continued, page 2 of 4)

#### **IMPORTANT SUBJECT INSTRUCTIONS:**

This is a "masked" clinical study in which the Investigators and Coordinators cannot see the Study Drops that are dispensed to you. There will be a special study employee – the "unmasked designee" – at the site who will dispense all study materials to you in a white drawstring bag and who will handle any questions you have related to the study materials.

It is very important that you keep your study drops in the opaque white bag when coming to the study visits.

#### **GENERAL INFORMATION:**

- Do NOT use any products other than those listed above or dispensed to you by your study doctor for use in this study.
- Do NOT use any other care products other than those listed above.
- Do not use any topical ocular medications (eye drops) during this study.
- Do NOT discuss or show the dispensed study products or these Subject Instructions to the study doctor or site staff other than the "unmasked designee" during the study.
- Save ALL study materials (drops and lenses) during the course of the study in the subject opaque drawstring take-home bag. Bring all opened and unopened study materials (drops and lenses) to the 1-month follow-up/exit visit. Place the multi-dose bottles or single-use dispensers, lens cases, and worn and unworn lenses into the white drawstring bag provided.
- Always wash and rinse your hands before you handle your lenses.
- Always handle the same lens (right or left) first, to avoid mix-ups.
- Always keep the products tightly closed when not in use.
- Lenses must be thoroughly cleaned, rinsed, and soaked using **Biotrue multi**purpose solution each time they are removed to achieve disinfection. See the Package Insert printed on the inside of the Biotrue multipurpose solution carton for important safety information.
- Rinse each case well with the **Biotrue multi-purpose solution** before and after each use.

#### **PRECAUTIONS**:

- Lens care procedures recommended by your study doctor must be followed.
- Failure to follow these procedures may result in the development of serious eye infections.
- Discard the **Biotrue multi-purpose solution** from the lens case after each use.
- Store **Study Drops and Biotrue multi-purpose solution** at room temperature. **SUBJECT INSTRUCTIONS (continued, page 3 of 4)**

- Use **Biotrue multi-purpose solution** before the expiration date marked on the bottle label and carton.
- Do not use any eye medication in conjunction with the **Study Drops** and **Biotrue multi-purpose solution** unless under medical supervision.
- Do not touch the tip of the **Study Drops** or **Biotrue multi-purpose solution** to any surface or to your eye since this may contaminate the study solutions.
- Keep the **Study Drops** and **Biotrue multi-purpose solution** cap closed when not in use to avoid contamination or evaporation.
- Do not use **Biotrue multi-purpose solution** with a heat disinfection method.
- Keep Study Drops and Biotrue multi-purpose solution out of reach of children.
- Consult with your study doctor if you have any allergies that may affect your ability to use the **Study Drops** or **Biotrue multi-purpose solution**.

#### **IMPORTANT**:

• If irritation or excessive tearing occurs, persists or increases, or if vision is impaired, discontinue use and promptly consult your study doctor.

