### 7.1.2.1 Anticipated Serious Adverse Device Effect (ASADE)

An ASADE is an ADE that first meets the serious criteria (see Section 7.1.3) or significant non-serious criteria (see Section 7.1.4) and which, by its nature, incidence,

severity or outcome, has been previously identified in the investigational plan or application (including a supplementary plan or application) and/or in the risk analysis report. ASADEs include:

- Corneal Ulcer (infectious or non-infectious)
- Keratitis
- Sensitivity to light (photophobia)
- Excessive eye secretions including mucopurulent discharge
- Blurred vision, rainbows or halos around objects
- Poor visual acuity (reduced sharpness of vision)
- Moderate to severe eye pain not relieved by removing the lens

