### 7.1.3 Serious Adverse Event (SAE)

An AE that:

- Led to death;
- o Led to serious deterioration in the health of the subject, that resulted in:
  - A life-threatening illness or injury; or
  - A permanent impairment of a body structure or a body function (e.g., blindness); or
  - Inpatient or prolonged hospitalization; or
  - Medical or surgical intervention to prevent life-threatening illness or injury or permanent impairment to a body structure or a body function;
- Led to fetal distress, fetal death, or a congenital abnormality or birth defect.

Note: A planned hospitalization for a pre-existing condition, or a procedure required by the protocol, without serious deterioration in health, is not considered an SAE.

Serious adverse events are also those events that result in, or have potential to cause, either permanent impairment of an ocular function or damage to an ocular structure and may necessitate medical or surgical intervention.

Serious adverse events may include any hazardous, sight-threatening conditions occurring after exposure to the test article, including the following:

- A presumed infectious ulcer (defined as a progressive erosion of the corneal tissue). For the purposes of reporting, this includes:
  - Central or para-central location;
  - o Penetration of Bowman's membrane;
  - o Infiltrate  $\geq 2$  mm diameter;

- Associated with iritis;
- o Associated with any increase in intraocular pressure;
- o Culture positive for microorganisms;
- o Increasing size or severity at subsequent visits;

NOTE: Signs of a presumed infectious corneal ulcer may include irregular focal infiltrates, active lesions with raised edges, significant diffuse infiltration, anterior corneal to mid-stromal involvement, erosion with overlying staining, conjunctival and lid edema, anterior chamber reaction (iritis), and severe bulbar and limbal redness. Symptoms associated with a presumed infectious ulcer (microbial keratitis) may include pain of rapid onset, severe redness, purulent or mucopurulent discharge, tearing, and photophobia.

- Any central or paracentral (within 6 mm of cornea) corneal event that results in permanent opacification (such as corneal scar or vascularization);
- Any serious adverse ophthalmic events including hypopyon and/or hyphema;
- Any neovascularization within the central 6 mm of the cornea;
- Permanent loss of >2 lines of BSCVA:
- All cases of iritis.

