#### **REWETTING DROP USAGE:**

Place study rewetting drops in each eye at least 4 times every day that lenses are worn during the one month you are in this study:

- During wear, place 1 to 2 study rewetting drops in the eye and blink. To avoid contamination, do not touch tip of container to any surface.
- As required by this study, always place drops in the eye 30 to 60 minutes before removing the lenses each day.
- If you have multi-dose bottles, replace the cap on the bottle after each treatment. Begin with "Bottle 1". When "Bottle 1" is empty place in zippered bag to return at exit visit. Open "Bottle 2" and continue to use until empty and place in zippered bag to return at exit visit. Continue to open the next sequential bottle when the last bottle opened becomes empty. Always keep products tightly closed when not in use. All bottles, used and unused will need to be returned at your exit visit.
- If you have single-use dispenser, to open, completely twist off tab and use one dispenser to treat both lenses at each treatment interval. Do not use the dispenser again after treatment even though there may be remaining drops in the dispenser. Place the used dispenser in the zipper bag to return at end of study. All single-use dispensers, used and unused will need to be returned at your exit visit.

Remember: It's important to wear your study lenses to each of your follow-up visits and place 1 to 2 drops of rewetting solution in each eye about 30-60 minutes before each scheduled study visit.

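### The one symptom-triggered stop-and-call line in both take-home sheets names neither discharge nor light sensitivity, and does not clearly tell the subject to remove the lenses

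*Combined protocol and SAP*

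**What the plan says.** Under IMPORTANT, Appendix E (soft lenses) and Appendix F (rigid lenses) carry the same line: "If irritation or excessive tearing occurs, persists or increases, or if vision is impaired, discontinue use and promptly consult your study doctor". No other line in either sheet links a symptom to an instruction to stop.

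Section 7.1.3 says that the symptoms of a presumed infectious ulcer "may include pain of rapid onset, severe redness, purulent or mucopurulent discharge, tearing, and photophobia". Section 7.1.2.1 lists anticipated serious adverse device effects. They include "Excessive eye secretions including mucopurulent discharge", light sensitivity, and "Moderate to severe eye pain not relieved by removing the lens".

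Under REWETTING DROP USAGE, both sheets tell the subject: "Place study rewetting drops in each eye at least 4 times every day that lenses are worn". The reminder that closes that part says it is "important to wear your study lenses to each of your follow-up visits", and the note at the top of each sheet says the same.

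**The concern.** The sheet is what the subject has at home. Section 3.4 schedules follow-up only around Day 15 and Day 31. The 24-hour reporting clock in Section 7.4 starts when the investigator becomes aware of an event. For a symptom that starts between visits, awareness will generally depend on the subject calling, and the IMPORTANT line is the one place in the sheet that says which symptoms call for it.

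Two things are wrong with that line. Its list of symptoms is shorter than the protocol's own list for the infection that matters most in lens wear. And it tells the subject to stop without saying what to stop. A subject who stops only the drops has followed one fair reading of it and could still have a lens on an inflamed eye. What is at stake is patient safety. No endpoint definition, sample-size figure, analysis or reporting rule depends on this line.

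**Working it through.** There is no figure in the plan to reproduce. The check is a reading of the whole of Appendices E and F against Sections 7.1.2.1 and 7.1.3 and Appendix B, Section 5.0.

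**Step 1: which lines prompt the subject to call or stop.** Each sheet has:
- one symptom-triggered stop-and-call line, under IMPORTANT, identical in the two sheets;
- one general line in the opening paragraph, telling the subject to consult the study doctor about any question or problem; it names no symptom and no stopping action;
- one allergy line under the precautions, triggered by a known allergy and not by a symptom;
- a warning that poor lens care can lead to serious eye infection, which lists no signs and gives no action.

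**Step 2: the ulcer symptoms of Section 7.1.3 against the line.**

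| Symptom in Section 7.1.3 | In the stop-and-call line? |
|---|---|
| Tearing | Named |
| Pain of rapid onset | Only if irritation is read broadly |
| Severe redness | Only if irritation is read broadly |
| Discharge | Not named |
| Photophobia | Not named |

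That is 1 named + 2 dependent on the reading + 2 not named = 5. Discharge and light sensitivity appear nowhere else in either sheet. The symptom form in Appendix B, Section 5.0 records photophobia separately from discomfort, itching/burning, excessive tearing and the vision items. The sponsor's own form therefore does not treat it as part of irritation or of impaired vision.

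**Step 3: what the subject is told to stop.** Three readings are open.
- All listed products. Each sheet opens its product section with the drops, the lenses and the other supplies that the subject will be using, so stopping use can include the lenses.
- The drops alone. This is the study product, and the precautions just before the line refer to it repeatedly.
- The drops and the care solution (Biotrue or Boston SIMPLUS). The same precautions pair the two.

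No line in either sheet tells a symptomatic subject to take the lenses out; lens removal is mentioned only as part of the daily routine. Drop use is tied to days of lens wear, but the sheet does not say the converse, that stopping the drops means stopping the lenses.

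**Step 4: the lines on wearing lenses to visits.** There are two in each sheet, with no exception for symptoms. They concern follow-up visits. Sections 6.1.2 and 6.1.3 say what to do when a subject arrives at a scheduled visit without lenses, and the unscheduled-visit procedure in Section 6.1.5 lets the site skip the on-eye lens evaluation in that case. These are instructions to the site, so they do not inform the subject, but they show that the protocol does not require a symptomatic subject to keep the lenses in.

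**The case against.** The strongest reply is that the sheet is one layer among several. Risks are explained before enrolment and in the consent process (Sections 4.9, 6.1 and 9.8.3). The sheet and the lens-wear warnings must be reviewed with the subject in person (Sections 4.3.2 and 6.4). Each sheet points twice to the care-solution package insert. The sheets need IRB approval (Section 9.8.1), unscheduled visits are available (Section 6.1.5), and subjects have worn their lens type for at least 3 months (Section 3.2.1.1). Any one of irritation, tearing or impaired vision triggers the line, so many subjects with a serious event would be prompted anyway. The lists in Section 7.1 serve the investigator's classification and reporting, and nothing requires the sheet to reproduce them. All of this stands, and it keeps the point minor. It does not supply the missing words or the missing object.

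Three stronger readings are tempting, and the documents do not support them.
- A reader might infer that subjects are never told about discharge, light sensitivity or lens removal. The consent form and inserts are not available here, and the content of the in-person review is not specified, so only the silence of the sheets is established.
- A reader might infer that the sheets tell a symptomatic subject to keep wearing the lenses. Step 4 shows that those lines concern follow-up visits, and Step 3 that lens removal is a possible reading of the stop instruction.
- A reader might take discharge or light sensitivity to be serious in itself because Section 7.1.2.1 lists it. That list applies only to device effects that first meet the serious or significant non-serious criteria.

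**Conclusion.** The point holds as a minor one about the wording of Appendices E and F. Two of the five ulcer symptoms in Section 7.1.3 are not named in the only symptom-triggered stop-and-call line, and two more depend on how irritation is read. Lens removal is a possible reading of the stop instruction but not a clear one.

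The sheets leave least guidance for a subject with discharge or light sensitivity but no irritation, excessive tearing or vision change. For that subject the sheet offers only its general line, which prompts a call but no stopping action. Nothing in the documents shows how often this would happen, and neither the number of subjects affected nor any delay can be estimated. The counts describe wording, not harm. The conclusion rests on the text of the two sheets alone and assumes nothing about the consent form, the inserts or what is said in person.

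**What to change.** In the IMPORTANT line of both appendices:
- add eye pain, marked redness, discharge and sensitivity to light to the triggers;
- replace the closing action with: *remove your lenses, stop the study drops and promptly contact your study doctor*.

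The clinical team should confirm the final wording.

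The change is one line per sheet plus IRB review of the revised sheets. It may bring a few more unscheduled visits. It may also slightly raise reports of photophobia, because the symptom question at visits is asked unprompted (Appendix B, Section 5.0: "The subject is not shown the list of options/descriptions") and the revised sheet would have named that symptom beforehand. The revised line would be the same in both arms, and that question is not a primary endpoint.
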